5.4.5 Dose Modification Guidelines

AEs (both serious and non-serious) potentially related to ANV419, pembrolizumab, or ipilimumab may represent an immunologic etiology. These AEs may occur shortly after the first dose or several months after the last dose.

If a patient experiences TEAEs that may be related to ANV419 alone or in combination with pembrolizumab or ipilimumab, ANV419 doses might be reduced if applicable, interrupted, or permanently discontinued and all changes must be reported in the Case Report Form (CRF). All ≥Grade 3 AEs considered possibly, probably, or definitely related to study drug(s) must be

discussed with the Investigator and Sponsor. During Cycle 1, dose interruption should be avoided if a patient has not experienced a ≥Grade 2 TEAE related to study drug. In subsequent cycles, dose interruptions and/or discontinuation are permissible following discussion between the Investigator and the Sponsor or designee.

5.4.5.1 Dose Modification and Management Guidelines for adverse events related to ANV419 in Monotherapy Arms

General principles

Common adverse events that have been reported with ANV419 include, but are not limited to pyrexia, liver enzyme elevations, lymphopenia, nausea/vomiting, and low-grade CRS. Appropriate supportive care or pre-medication is recommended to manage ANV419 related side effects, and to maintain ANV419 dose-intensity.

For patients enrolled in Arm A1 (), dose reduction is not permitted but modification of infusion rate and/or dose delay is allowed in the event of ANV419 related toxicities. For patients enrolled in Arm A2 (), dose reduction to is permitted in addition to modification of infusion rate and/or dose delay. Dose re-escalation of ANV419 to the randomized dose can be considered for AEs that are self-limiting and under close monitoring. If re-escalation is not tolerated, then ANV419 should be reinstated at reduced dose.

Treatment may be delayed for up to ______ to allow for resolution of ANV419 related toxicities and for up to ______ for non-ANV419 related/unexpected toxicities (i.e., hip fracture). If treatment cannot be resumed within this time frame, the patient will be permanently discontinued from study.

The section below provides specific guidelines for the management of related ANV419 toxicities. The recommendations are not intended to serve as rigid guidelines or to replace clinical judgement.

Pyrexia

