Transient elevation of hepatic transaminases are observed with ANV419 and are considered to occur in the context of IL-2 mediated AEs. The transient elevations are usually asymptomatic, mild or moderate in severity, typically not associated with increased total bilirubin and alkaline phosphatase, resolve spontaneously without treatment, and are predominantly occurring in the first two cycles. For AST and/or ALT elevations beyond cycle 2, and for AST/ALT elevations in the

context of total bilirubin increase, follow the adverse event management guidance for hepatitis (Table 15).

Table 14: Management guidelines for AST and/or ALT elevations with early onset related to ANV419

	Recommended management	Dose modification
AST or ALT > 3 but ≤ 5 × ULN	 LFT monitoring: Repeat lab every 3 days If no improvement within 7 days, initiate treatment with steroids Consider imaging for obstruction Exclude non-inflammatory etiologies 	Withhold ANV419 until ≤ Grade 1 or baseline; continue at same dose
AST or ALT > 5 × but ≤ 8 × ULN	 LFT monitoring: Repeat lab every 3 days If no improvement within 7 days, initiate treatment with steroids Consider adding non-corticosteroid immunotherapy 	Withhold ANV419 until ≤ Grade 1 or baseline; continue at same dose
AST or ALT > 8 × ULN	 LFT monitoring: Repeat lab every 1-2 days If no improvement within 7 days, initiate treatment with steroids Consider adding non-corticosteroid immunotherapy Consult gastroenterologist 	Consider permanent discontinuation of ANV419

Hepatitis

Table 15: Management guidelines for hepatitis related to ANV419

(adapted from the ASCO management guidelines for Immune-Related Adverse Events; J Clin Oncol2021:36 4073-4126).

CTCAE v5.0	Recommended management	Dose modification
Grade 1	• Close monitoring (1-2 ×	Continue ANV419 at same dose
Asymptomatic (AST or	weekly)	
ALT > ULN to $3.0 \times$	• Exclude alternate etiologies	
ULN and/or total	(e.g., viral hepatitis, alcohol	
bilirubin > ULN to 1.5 ×	hepatitis)	
ULN	1 /	

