5.4.5.4 Management of adverse events in combination arms

AEs associated with pembrolizumab or ipilimumab exposure may represent an immunologic etiology. These irAEs may occur shortly after the first dose or several months after the last dose of pembrolizumab/ipilimumab treatment and may affect more than 1 body system simultaneously. Therefore, early recognition and initiation of treatment is critical to reduce complications. Based on existing clinical study data, most irAEs were reversible and could be managed with interruptions of pembrolizumab or ipilimumab, administration of corticosteroids, and/or other supportive care. For suspected irAEs, ensure adequate evaluation to confirm etiology or exclude other causes. Additional procedures or tests such as bronchoscopy, endoscopy, or skin biopsy may be included as part of the evaluation. Based on the severity of irAEs, withhold or permanently discontinue pembrolizumab/ipilimumab, and administer corticosteroids. Consultation with disease-specific specialists should be considered. Dose modification and toxicity management guidelines for irAEs associated with pembrolizumab and ipilimumab are provided in Table 18 and Table 19, respectively.

Attribution of toxicity and holding study drugs

When study drugs are administered in combination, attribution of an AE to a single component is likely to be difficult. Therefore, while the Investigator may attribute a toxicity event to the combination, to ANV419 alone, to pembrolizumab alone, or to ipilimumab alone, for AEs listed in Table 18 and Table 19, both interventions must be held according to the criteria in Table 18 and Table 19.

For AEs that occur with the combination of ANV419 and pembrolizumab or ANV419 and ipilimumab that clearly can be attributed to ANV419, please refer to Section 5.4.5 for management guidelines and recommended dose modifications to be taken for ANV419.

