For combination arms of this study, both drugs should be held until the attribution of an irAEs can be fully analyzed and has resolved to baseline or ≤Grade 1. In general, ≥Grade 3 TEAEs in the combination treatment arms will result in discontinuation of both ANV419 and pembrolizumab or ANV419 and ipilimumab, but, in rare instances, continuing either ANV419, pembrolizumab, or ipilimumab may be allowed where clinical benefit can be documented after resolution of toxicity to baseline or ≤Grade 1. In the event that a toxicity results in holding ANV419, pembrolizumab, ipilimumab, or the combination of ANV419 and pembrolizumab or the combination of ANV419 and ipilimumab for >42 days, the drugs should be permanently discontinued for that patient.

Table 18. Dose Modification for ANV419 in Combination With Pembrolizumab

Table 10. Dose		UI AITTI	ii Combination	vitn Pembrolizu	mab
	Grade			Corticosteroid	
	(NCI CTCAE	Action with	Action with	and/or Other	Monitoring and
irAEs	Version 5.0)	ANV419	Pembrolizumab	Therapies	Follow-Up
Pneumonitis	Grade 2 Recurrent Grade 2, Grade 3 or 4	Withhold. Upon resolution to ≤Grade 1, may resume study treatment. Withhold study treatment. Upon resolution to ≤Grade 1, may resume study treatment 1 dose level	Withhold. Upon resolution to ≤Grade 1, may resume study treatment. Permanently discontinue.	Administer corticosteroids (initial dose of 1 to 2 mg/kg prednisone or equivalent) followed by taper. Add prophylactic antibiotics for opportunistic infections.	Monitor participants for continuing signs and symptoms of pneumonitis. Evaluate participants with radiographic imaging

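### Section 5.4.5.4 gives overlapping instructions for liver-enzyme rises attributed to ANV419 in the combination arms: one route restarts ANV419 at the same dose where Tables 18 and 19 stop it for good

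*Protocol*

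**What the plan says.** Two consecutive paragraphs of Protocol Section 5.4.5.4, under the subheading on attribution of toxicity, address an event that the investigator ascribes to ANV419.

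- **First paragraph.** It recognises that an event may be attributed to the combination or to one drug, including ANV419 alone. For events listed in Tables 18 and 19 it then says that "both interventions must be held according to the criteria in Table 18 and Table 19".
- **Second paragraph.** It covers combination-arm events "that clearly can be attributed to ANV419, please refer to Section 5.4.5 for management guidelines and recommended dose modifications to be taken for ANV419". It makes no exception for events listed in the two tables.

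The text that follows sets a default for Grade 3 and above: in general, "Grade 3 TEAEs in the combination treatment arms will result in discontinuation of both ANV419 and pembrolizumab", and likewise for the ipilimumab pair. Its exception is narrow: "in rare instances, continuing either ANV419, pembrolizumab, or ipilimumab may be allowed where clinical benefit can be documented after resolution of toxicity" to baseline or Grade 1 or lower.

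Within Section 5.4.5, the ANV419-specific management tables (Tables 12 to 16) are in 5.4.5.1, titled "Dose Modification and Management Guidelines for adverse events related to ANV419 in Monotherapy Arms". Its general principles add: "The recommendations are not intended to serve as rigid guidelines or to replace clinical judgement". Early transaminase rises are said there to be transient and "are considered to occur in the context of IL-2 mediated AEs". Table 14 manages them and has a row for "AST or ALT > 5 × but ≤ 8 × ULN".

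Tables 18 and 19 each have a named row for AST/ALT elevation. Both tables are headed as irAE tables, and their notes leave non-irAEs to clinical practice.

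**The concern.** AST/ALT elevation has its own row in both combination tables, and it is also an event that an investigator could confidently ascribe to ANV419. Such an event meets the conditions of both paragraphs. If they led to the same action, the overlap would be harmless, but in one band of values the ANV419 actions are opposite: restart at the same dose, or stop permanently.

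A site following the second paragraph to the ANV419 liver guidance could restart ANV419 after a liver event that the combination tables treat as final. Table 14 does not ask for the documented clinical benefit that Section 5.4.5.4 requires before a drug may continue after a Grade 3 event.

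**Working it through.** The plan gives no figure to reproduce. The check compares the actions and thresholds of the three tables.

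**1. Scope of Table 14.** It covers AST/ALT rises in Cycles 1 and 2. Section 5.4.5.1 sends later rises, and rises with raised bilirubin, to Table 15, which stops ANV419 permanently at Grade 3. The comparison therefore concerns isolated rises in Cycles 1 and 2.

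**2. Action on ANV419 by AST/ALT level.**

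| AST/ALT | Table 14 | Table 18 (Arm B), normal baseline | Table 19 (Arm C) |
|---|---|---|---|
| >3 to 5 x ULN | Pause, restart at same dose | Pause, may resume | Pause, may resume |
| >5 to 8 x ULN | Pause, restart at same dose | Stop permanently | Stop permanently |
| >8 x ULN | Consider stopping permanently | Stop permanently | Stop permanently |

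The first row is compatible across the tables. In the second the actions are opposite. In the third, Table 14 is advisory and the other two are mandatory.

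**3. Effect of an abnormal baseline.** Table 19 uses multiples of ULN only, so the conflict in Arm C covers the whole band of >5 to 8 x ULN at any baseline. The notes to Table 18 define Grade 3 as >5 to 20 x ULN with a normal baseline and >5 to 20 x baseline with an abnormal one. For an abnormal baseline of b x ULN:

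- Grade 3 starts above 5b x ULN.
- Overlap with the Table 14 row is >5b to 8 x ULN.
- The overlap is non-empty only if 5b < 8, that is, b < 8/5 = 1.6.

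| Baseline b (x ULN) | 5b | Conflict within the >5 to 8 x ULN row, Arm B |
|---|---|---|
| Normal | 5 (ULN-based) | >5 to 8 x ULN |
| 1.2 | 6.0 | >6 to 8 x ULN |
| 1.5 | 7.5 | >7.5 to 8 x ULN |
| 1.6 | 8.0 | None |
| 2.5 (eligibility limit without liver metastases) | 12.5 | None |

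**4. Where the second paragraph leads.** It promises management guidelines and recommended dose modifications for ANV419, which closely matches the title of 5.4.5.1. The opening of Section 5.4.5 says only in general terms that ANV419 may be reduced, interrupted or discontinued, and has no liver-specific instruction. Table 14 is therefore where a reader looking for ANV419 liver guidance would arrive.

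**5. Frequency.** Protocol Section 1.3.4, Table 1, reports related Grade 3 or higher AST increase in 2/34 patients (5.9%) and ALT increase in 1/34 (2.9%) in ANV419-001. This is monotherapy, and the available text does not give cycle, bilirubin, baseline or peak value for these cases. The figures show that such events occur and cannot be turned into a rate for Arms B and C.

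**The case against.** The strongest reply is that the protocol, read as a whole, already settles the matter.

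- The first paragraph is mandatory and names attribution to ANV419 alone, while the second only refers the reader elsewhere. The Grade 3 default that follows has no carve-out by attribution.
- Scope is set by subsection heading. Sections 5.4.5.1 and 5.4.5.2 are for the monotherapy arms, and 5.4.5.3, on cytokine release syndrome, is expressly for both settings. On that reading Table 14 never reaches Arms B and C.
- The second paragraph still has content without Table 14, through the opening of Section 5.4.5 and Table 17.
- The opening of Section 5.4.5 also requires Grade 3 or higher related events to be discussed with the sponsor.
- In Part 2, early liver events may also be covered by the DLT definitions, which are not visible. SAP Section 3.8.1.1 lists laboratory abnormalities and drug-induced liver injury among the DLT types.

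Much of this stands. The reading that Tables 18 and 19 control is the better supported one, and the sponsor discussion is a real safeguard. However, the protocol nowhere says that the second paragraph is confined to unlisted events. The irAE heading and the note on non-irAEs, together with the description of early rises as IL-2 mediated, give an investigator a respectable reason to treat the event as outside those tables. The first paragraph goes by listed event and not by immune cause, which answers that reason only by inference.

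A reader might go further and infer that the protocol authorises full-dose rechallenge after Grade 3 hepatotoxicity in the combination arms, or that patients or dose selection were affected. The documents do not support either. The mandatory wording and the default point the other way, and SAP Section 1 records that the trial stopped at the end of Part 1.

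**Conclusion.** The wording conflict is real but minor. For an isolated Cycle 1 or 2 AST/ALT rise attributed to ANV419, the two routes prescribe opposite ANV419 actions at >5 to 8 x ULN: over the whole band in Arm C, and in Arm B over the whole band with a normal baseline, narrowing to nothing at a baseline of 1.6 x ULN. Above 8 x ULN the difference is between considering discontinuation and requiring it, in Arm B wherever Table 18's Grade 3 or 4 is reached.

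The conclusion assumes that a site following the second paragraph would take 5.4.5.1 as its target, which is natural but not stated. No patient count is projected, and no effect on RP2D or on the trial as run is claimed. The point matters only if the combination parts open or the text is reused.

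**What to change.** 1. Open the second paragraph with a limiting clause, keeping the rest of the sentence: *For AEs without their own named row in Table 18 or Table 19 (that is, other than the catch-all row for all other irAEs)*. Going by named row follows the first paragraph's logic. Mentioning the catch-all row is necessary because both tables end with one, which makes a bare reference to unlisted events unclear.
2. Add one sentence stating that in Arms B and C the AST/ALT rows of Tables 18 and 19 apply, not Table 14.
3. If the sponsor does intend rechallenge after a transient IL-2 mediated rise, write it into those AST/ALT rows as an explicit exception with stated limits.

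Under step 1, an event that falls only in the catch-all row goes to Section 5.4.5 when it is clearly due to ANV419. If that is not wanted, the sponsor should say so.

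**Cost.** One clause and one sentence, with no change to design, sample size or data collection. The substantial amendment that Protocol Section 3.1.2 requires before Part 2 could carry it. The clinical downside of steps 1 and 2 without step 3 is that some patients with transient, reversible rises would stop treatment.

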Pneumonitis	Grade 2 Recurrent Grade 2, Grade 3 or 4	Withhold. Upon resolution to ≤Grade 1, may resume study treatment. Withhold study treatment. Upon resolution to ≤Grade 1, may resume study treatment 1 dose level lower.	Withhold. Upon resolution to ≤Grade 1, may resume study treatment. Permanently discontinue.	Administer corticosteroids (initial dose of 1 to 2 mg/kg prednisone or equivalent) followed by taper. Add prophylactic antibiotics for opportunistic infections.	Monitor participants for continuing signs and symptoms of pneumonitis. Evaluate participants with radiographic imaging.

Table 19. Dose Modification for ANV419 in Combination With Ipilimumab (Continued)

Table 19. Dose	Modification 10	or AN V 419 in	Combination V	Vith Ipilimumab	(Continuea)
irAEs Diarrhea/colitis	Grade (NCI CTCAE Version 5.0) Grade 2 Recurrent Grade 3 or Grade 4	Action with ANV419 Withhold. Upon resolution to ≤Grade 1, may resume study treatment.	Action with Ipilimumab Withhold. Upon resolution to ≤Grade 1, may resume study treatment.	Corticosteroid and/or Other Therapies Administer corticosteroids (initial dose of 1 to 2 mg/kg prednisone or equivalent) followed by taper.	Monitoring and Follow-Up Monitor participants for continuing signs and symptoms of enterocolitis (ie, diarrhea, abdominal pain, blood or mucus in stool with or without fever) and of bowel perforation (ie, peritoneal signs and ileus). Participants with ≥Grade 2 diarrhea suspected colitis should consider GI consultation and performing endoscopy to rule out colitis. Participants with diarrhea/colitis should be advised to drink liberal quantities of clear fluids. If sufficient oral fluid intake is not feasible, fluid and electrolytes should be substituted via IV infusion.
AST or ALT elevation or increased bilirubin	AST/ALT >3 to 5 × ULN or total bilirubin is more than 1.5 × and up to 3 × ULN AST/ALT >5 × ULN or total bilirubin is more than 3 × ULN	Withhold. Upon resolution to ≤Grade 1, may resume study treatment. Permanently discontinue.	Withhold. Upon resolution to ≤Grade 1, may resume study treatment. Permanently discontinue.	Administer corticosteroids (initial dose of 0.5 to 1 mg/kg prednisone or equivalent) followed by taper. Administer corticosteroids (initial dose of 1 to 2 mg/kg prednisone or equivalent) followed by taper.	Monitor with liver function tests (consider weekly or more frequently until liver enzyme value returned to baseline or is stable).

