Table 19. Dose Modification for ANV419 in Combination With Ipilimumab (Continued)

Table 19. Dose	Modification id	or AN V 419 in	Combination v	Vith Ipilimumab	(Continued)
	Grade			Corticosteroid	
	(NCI CTCAE	Action with	Action with	and/or Other	Monitoring and
irAEs	Version 5.0)	ANV419	Ipilimumab	Therapies	Follow-Up
Endocrinopathies	Grade 2, 3, or 4	Withhold. Upon resolution to ≤Grade 1, may resume study treatment.	Withhold if not clinically stable.	Treatment with replacement or interventions as appropriate.	Monitor for signs and symptoms of endocrinopathies.
Hypophysitis ¹	Grade 2, 3, or 4	Withhold. Upon resolution to ≤Grade 1, may resume study treatment.	Withhold. Resume when acute symptoms have resolved.	Administer corticosteroids and initiate hormonal replacements as clinically indicated.	Monitor for signs and symptoms of hypophysitis (including hypopituitarism and adrenal insufficiency).
Nephritis: with renal dysfunction	Grade 2 or 3 increased blood creatinine Grade 3 or 4	Withhold. Upon resolution to ≤Grade 1, may resume study treatment. Permanently discontinue.	Withhold. Upon resolution to ≤Grade 1, may resume study treatment. Permanently discontinue.	Administer corticosteroids (prednisone 1 to 2 mg/kg or equivalent) followed by taper.	Monitor changes of renal function.
Neurological toxicities ²	Grade 2 Grade 3 or 4	Withhold. Upon resolution to ≤Grade 1, may resume study treatment. Permanently discontinue.	Withhold. Upon resolution to ≤Grade 1, may resume study treatment. Permanently discontinue.	Based on severity of AE, administer corticosteroids.	Ensure adequate evaluation to confirm etiology and/or exclude other causes.
Myocarditis	Grade 2 Grade 3 or 4	Withhold. Upon resolution to ≤Grade 1, may resume study treatment. Permanently discontinue.	Withhold. Upon resolution to ≤Grade 1, may resume study treatment. Permanently discontinue.	Based on severity of AE, administer corticosteroids.	Ensure adequate evaluation to confirm etiology and/or exclude other causes.
Exfoliative or bullous dermatologic conditions	Grade 2 Grade 3 or 4	Withhold until specialist assessment. Permanently discontinue.	Withhold until specialist assessment. Permanently discontinue.	Based on severity of AE, administer corticosteroids.	Ensure adequate evaluation to confirm etiology or exclude other causes.

Table 19. Dose Modification for ANV419 in Combination With Ipilimumab (Continued)

				, ich ipilinamas	(

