irAEs	Grade (NCI CTCAE Version 5.0)	Action with ANV419	Action with Ipilimumab	Corticosteroid and/or Other Therapies	Monitoring and Follow-Up
Ophthalmologic	Grade 2, 3, or 4 that does not improve to Grade 1 within 2 weeks while receiving topical therapy or that requires treatment	Withhold or discontinue based on the event.	Permanently discontinue.	Based on recommendation by ophthalmologist.	Ensure evaluation by ophthalmologist and continue to follow up as clinical indicated.
All other irAEs	Persistent Grade 2 Grade 3 Recurrent Grade 3 or Grade 4	Withhold. Upon resolution to ≤Grade 1, may resume study treatment. Withhold or discontinue based on the event. Permanently discontinue.	Withhold. Upon resolution to ≤Grade 1, may resume study treatment. Withhold or discontinue based on the event. Permanently discontinue.	Based on severity of AE, administer corticosteroids.	Ensure adequate evaluation to confirm etiology or exclude other causes.

Note: Non-irAEs will be managed as appropriate, following clinical practice recommendations.

- 1. Signs of mass effect, including headache, photophobia, or visual field cuts.
- 2. Permanently discontinue ipilimumab if signs of encephalitis or respiratory insufficiency due to neurological toxicity regardless of grade.

AE = adverse event; ALT = alanine aminotransferase; AST = aspartate aminotransferase; GI = gastrointestinal; irAE = immune-related adverse event; IV = intravenous(ly); NCI CTCAE = National Cancer Institute Common Terminology Criteria for Adverse Events; ULN = upper limit of normal.

Source: Yervoy®. Package Insert. Bristol-Myers Squibb Company; 2011

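### Table 19's nephritis row (Arm C) puts Grade 3 under both rechallenge and permanent discontinuation, and does not name what the second tier grades

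*Protocol*

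**What the plan says.** Protocol section 5.4.5.4 makes Tables 18 and 19 binding for holding study drugs in the combination arms. Table 19 covers ANV419 with ipilimumab. Its row for nephritis with renal dysfunction gives two grade tiers, "Grade 2 or 3 increased blood creatinine Grade 3 or 4". The ANV419 and ipilimumab columns carry the same two actions: withhold, with resumption allowed once the event is down to Grade 1 or lower; and permanent discontinuation. The grade column is headed NCI CTCAE version 5.0.

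Three general provisions also bear on the row:

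- Section 5.4.5.4: "In general, ≥Grade 3 TEAEs in the combination treatment arms will result in discontinuation of both ANV419 and pembrolizumab or ANV419 and ipilimumab". The same sentence adds that "in rare instances, continuing either ANV419, pembrolizumab, or ipilimumab may be allowed where clinical benefit can be documented", once toxicity has returned to baseline or Grade 1 or lower.
- Section 5.4.5.4: if toxicity leads to a hold of ">42 days, the drugs should be permanently discontinued for that patient".
- Section 5.4.5: all "≥Grade 3 AEs considered possibly, probably, or definitely related to study drug(s) must be" discussed with the investigator and the sponsor.

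**The concern.** A dose-modification table should give one instruction for each grade. Here a patient with Grade 3 renal toxicity meets a tier that allows both drugs to restart and a tier that forbids it. Two sites could handle the same patient in opposite ways and each cite the table. The mandatory sponsor discussion reduces that risk, but it supplies no criterion for choosing between the two answers. What is at stake is rechallenge after severe renal toxicity. No endpoint, error rate or sample size depends on it.

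**Working it through.** No calculation in the plan is involved; the check is a reading of the row against everything that might settle it.

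**The tiers.** First tier = {2, 3}; second tier = {3, 4}. The intersection is {3}.

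| Grade | First tier | Second tier | Instruction for both drugs |
|---|---|---|---|
| 2 | yes | no | withhold, may resume |
| 3 | yes | yes | may resume, and permanently discontinue |
| 4 | no | yes | permanently discontinue |

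**Splitting the cell.** Sub-rows are merged in the text available for this review, so tiers were matched to actions by order. The words about blood creatinine occur once. They belong most naturally to the first tier, but attaching them to the second leaves the sets {2, 3} and {3, 4} unchanged. The overlap does not depend on where the cell is divided.

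**Places that might resolve it:**

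- *Column header.* It fixes the grading system, CTCAE version 5.0. It does not say which parameter the unlabelled tier grades.
- *Footnotes to Table 19.* There are two. The first reads "Signs of mass effect, including headache, photophobia, or visual field cuts" and is attached to hypophysitis. The second concerns neurological toxicity. Neither touches nephritis.
- *A recurrence qualifier.* The catch-all row at the end of Table 19 separates a Grade 3 event from a recurrent Grade 3 or a Grade 4 event. The nephritis row has no such word.
- *Table 18 (pembrolizumab).* Its nephritis row names what is graded and splits cleanly into Grade 2 and Grade 3 or 4. It cannot be taken as evidence of what Table 19 intended, because the tables differ elsewhere: Grade 2 myocarditis means permanent discontinuation in Table 18 and possible resumption in Table 19.
- *The general rule for Grade 3 or higher.* It leans towards stopping but is qualified in its own wording. Table 19 also departs from it in other rows. After Grade 3 or 4 pneumonitis the ANV419 instruction is "may resume study treatment 1 dose level lower". For Grade 2 to 4 hypophysitis the ipilimumab instruction is "Withhold. Resume when acute symptoms have resolved". If the general rule overrode this row on a single scale, naming Grade 3 in the first tier would have no effect.

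**What is left open.** Both tiers stop both drugs immediately, and a hold beyond 42 days ends treatment in any case. The contradiction is confined to a Grade 3 patient who recovers to Grade 1 or lower within 42 days.

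**The case against.** The best defence is that the tiers grade different things: the first a creatinine value, the second the nephritis event. The reference to Grade 3 in the first tier would then keep a use (Grade 3 creatinine with Grade 2 nephritis), and a patient meeting both tiers would follow the more severe one. Table 19's liver row needs the same convention: AST at 4 × ULN with bilirubin at 4 × ULN meets its lower tier on AST and its upper tier on bilirubin. This stands to the extent that one should not claim the row is beyond rescue on a two-parameter reading. But the row states neither the second parameter nor the convention.

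A second defence is that 5.4.5.4 already supplies a default (stop) and a conditioned exception (documented benefit), and that explicit departures in other rows do not weaken it where a row is unclear. Further, the first tier only permits resumption, so a site that always discontinued at Grade 3 would breach neither tier. This is a good reason to make discontinuation the default in the fix. It does not remove the conflict, because the nephritis row is itself a specific instruction that lists Grade 3 as eligible to resume on recovery alone.

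A third is that text may have been lost in reading the PDF; the colitis row of Table 19, for instance, shows two tiers but only one action per drug. A dropped qualifier cannot be excluded from the extracted text, and the printed table should be checked. Merging of sub-rows alone does not produce the overlap.

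A reader might also infer that the row gives no grading system at all. It does: CTCAE is in the header and creatinine is named once. Only the second tier's parameter is missing.

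**Conclusion.** The point holds as a minor inconsistency in a binding safety table. Grade 3 carries opposite rechallenge instructions for both drugs in one row of one arm, and the graded parameter is named for only one tier. This rests on the row being complete as extracted and on tiers and actions being matched in order.

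Two stronger inferences are not supported. One is that sites would not know whether to stop treatment; both tiers stop it. The other is that patients or results were affected. SAP section 1 records the decision of 27 February 2024 to stop at the end of Part 1, and SAP section 5 drops all Part 2 and Part 3 analyses, so Arm C never opened. The documents give no rate for this event and do not show which split was intended. The point matters for the correctness of the protocol text and for any reuse of the table.

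**What to change.** Make the tiers mutually exclusive and name the graded parameter in each.

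- **Default, consistent with 5.4.5.4:** Grade 2 increased blood creatinine, withhold and may resume at Grade 1 or lower; Grade 3 or 4 increased blood creatinine, permanently discontinue.
- **If the sponsor intends rechallenge after Grade 3 creatinine:** Grade 2 or 3 against Grade 4, stated in the row as an exception to the general Grade 3 rule.
- **If two parameters are intended:** label each tier with its own parameter and state that the more severe tier governs.

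The sponsor has to choose. The edit is to one table cell and has no effect on sample size, data collection or analysis. It could have gone into the substantial amendment that Protocol section 3.1.2 already required before Part 2.
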